### ***Long-term Quitting Study***

Initial Cessation Treatment. The Initial Cessation Treatment, which meets the standard of care, will include 3 counseling contacts: one 10-minute in-person counseling session 1 week prior to the quit day, and 5 min counseling calls 1 and 2 weeks post-quit. The counseling content will be supportive and will include some skill development as recommended by the 2008 PHS Guideline (Fiore et al., 2008). The counseling will include encouragement and will also emphasize the importance of taking the medication and how to use it, and provide information about side effects/safety and what to do in case of problems. Participants will receive 8 weeks of nicotine patch (participants who smoke >10 cigs/day: 4 weeks of 21 mg, 2 weeks of 14 mg, and 2 weeks of 7 mg nicotine patches; participants who smoke ≤10 cigs/day: 6 weeks of 14 mg and 2 weeks of 7 mg nicotine patches). Participants will receive their medication at Visit 1 (i.e., 1 week before the quit day).

Relapse Recovery Phase. If participants relapse within 6 months of their Initial Cessation treatment quit day, they will be eligible to receive RR Preparation treatment unless they have been randomized to the RR Preparation Control condition. Relapse will be defined as 7 consecutive days of smoking at any point after the quit day. Relapse will be detected via counseling calls and Initial Cessation phase assessment calls (see Table 6). Participants will

“Breaking Addiction to Tobacco for Health (BREATHE) Study”

PI: [name], MPH, MBA; UW-CTRI Center Grant: 1P01CA180945-01.

also be asked to call the program office if they return to daily smoking. Participants in the Relapse Recovery Preparation Phase (and not in the RR Preparation Control condition) will be randomized to one of two treatments: Behavioral Reduction Counseling + Nicotine Replacement Therapy (NRT with the nicotine mini-lozenge) or Recycling Counseling.

**Table 9. Counseling contacts for the Relapse Recovery Preparation Phase Components.**

	Wk 0	Wk 2	Mo 1	Mo 3	Mo 6	Mo 9	Mo 11
RR Reduction Counseling (All calls 15 min; 30 min Visit 1; 20 min at Visit 2 and 3)	V1	C1	V2	C2	V3	C3	C4
RR Recycling Counseling (20 min at V1; 15 min at V2, 10 min at V3; all others are 5-10 min)	V1	C1	V2	C2	V3	C3	C4

*Note: C = Calls V = Visits RR Reduction Counseling and Nicotine Replacement Therapy.*

Participants randomized to this treatment will receive manual-based counseling calls and visits over the course of 11 months (see Table 9). The ultimate goal will be smoking that is reduced in amount and location. Case managers and participants will collaboratively identify a set of steps to progressively reduce smoking (e.g., make the house smoke-free). The primary vehicles for change are to encourage substitution of the nicotine mini-lozenge for cigarettes and to reduce the contexts in which smoking occurs (including making the home smoke free). Counseling will counter post-lapse demoralization by emphasizing participants’ progress, the value of smoking *reduction* as a transitional goal, and the critical value of ongoing treatment engagement. Evidence of progress in reduction of smoking, and smoking contexts will be used to build self-efficacy. Case managers will monitor the outcomes of these tasks, provide feedback to patients on their status over time and help participants attribute their success to their own efforts.

Participants will also receive up to 11 months of mini-lozenges as part of this treatment (dosing based on their nicotine dependence as measured when they started the study: 4 mg if they smoked within 30 minutes of waking and 2 mg if they smoked more than 30 minutes after waking, as per the package insert), along with instructions for use. Starting Spring 2018 we started to screen individuals who would be prescribed mini-lozenges for soy allergens prior to dissemination to prevent allergic reaction AEs - per the ML new package insert. Participants will receive 2 months of mini-lozenges at the Week 0 visit, 2 months of mini-lozenges at the Month 1 visit, 3 months of mini-lozenges following the counseling call at Month 3, and the last 4 months of mini-lozenges at the Month 6 visit. *If participants don’t attend the RR Reduction Counseling V1, V2, or V3 but they indicate that they want mini-lozenges, we will mail the mini-lozenges to them.* Participants will be able to switch to a lower dose of mini-lozenges over the course of Reduction Therapy if the Medication Safety Assessment suggests this could be helpful. Participants will be encouraged to use around 9 lozenges/day for the duration of time they are in Reduction therapy. If adherence data suggest low usage, the health counselor will work with the participant to identify barriers to use. Participants will also be asked about the occurrence of side effects. Participants will be told that if they are using the mini-lozenge regularly and are smoking in only a limited number of contexts, they are building success for their quit attempt. The intent is *to convey a realistic and positive appraisal of participants’ increasing ability to control their smoking.*

After 1 month of treatment, at every RR Reduction Counseling contact case managers will offer participants the option of beginning RR Cessation treatment. However, care will be taken

## PROTOCOL

### “Breaking Addiction to Tobacco for Health (BREATHE) Study”

PI: [name], MPH, MBA; UW-CTRI Center Grant: 1P01CA180945-01.

to ensure that participants do not feel pressured to make a quit attempt before they are ready.

*RR Recycling Counseling.* Participants assigned to this treatment condition will also have 7 treatment contacts (see Table 9) and will be encouraged to commit to a quit date as soon as they feel ready. As in prior recycling efforts, participants will be encouraged to discuss reasons for quitting, concerns and barriers, and to view abstinence as the primary treatment goal.

To ensure all participants remember they can make a quit attempt with study help at any time, participants in both the RR Reduction and Recycling Conditions will receive letters, emails, or text messages (depending on the preferred delivery route they selected at the start of the study and depending on what is feasible) at Weeks 10, 32, and 41 encouraging them to make a quit attempt and providing information on how to contact study staff to receive RR Cessation treatment.

RR Cessation or “New Quit” Phase. When participants opt to make a new quit attempt within 11 months of entering the RR Preparation Phase, they will be transitioned to RR Cessation treatment. RR Cessation Phase participants will be randomized to one of 4 treatment conditions (a 2x2 factorial design) comprising 2 active intervention components: 1) Skill-Based Training vs. Brief Information; and 2) Supportive Counseling vs. Brief Information. Each form of counseling is designed to boost cessation success through the incorporation of medication adherence content: i.e., the importance of using medication despite lapsing, inculcating positive beliefs about medication, and so on. Participants will receive skill-based, supportive counseling or both prior to and after discontinuation of study medication, including supportive maintenance phone calls. Elements of this counseling will be designed to ease the transition off medication.

The delivery of *each active* counseling component (i.e., Skill-Based Training or Supportive Counseling) will take 15-20 minutes at Visit 1, 15 minutes at Visit 2 and 10-15 minutes/call. The RR Cessation Brief Information intervention will take about 5 minutes/contact and occur at Visit 1 and 2 and the Target Quit Day. When a participant receives both of the active components the net delivery time will be 35-45 minutes for each visit and 20-25 min/call to ensure that the Brief Information content is also covered (see Table 10).

**Table 10. Long-Term Quitting Study RR Cessation (“New Quit”) Phase Counseling**

Week	-1	Day -2	0 (TQD)	1	2	3	6	8.5	14	Total Contact Time
Visit or Call	V	C	C	V*	C	C	C	C	C	
# Minutes Brief Info Only	5		5	5						15
# Minutes Support or Skill Training + Brief Info	20-25	10-15	15	20	10	10	10	10	10	115-125
# Minutes Support + Skill Training + Brief Info	35-45	20-25	25	35	20	20	20	20	20	215-230

\*This is a call for the Brief Info Only Group. TQD = Target Quit Day

*Brief Information.* All participants will receive brief (generic) information about the importance of taking the medication and how to use it, information about side effects/safety and what to do in case of problems, and will also be given encouragement.

“Breaking Addiction to Tobacco for Health (BREATHE) Study”

PI: [name], MPH, MBA; UW-CTRI Center Grant: 1P01CA180945-01.

*Skill Training Therapy.* Skill training therapy will: 1) carefully assess smoking cue contexts and opportunities to smoke, concentrating especially on problems encountered in the participant’s prior quit attempt; 2) develop specific plans for avoiding such contexts and skills for coping with them; 3) help participants develop plans for negotiating with critical others who smoke (e.g., housemates, co-workers); 4) develop lifestyle changes to reduce future smoking opportunities and contexts; and 5) assign homework and assess execution of assigned skills. Participants will also receive coping menus that the counselor fills out with the patient that provide personalized coping/avoidance options and “coping reports” that assess coping execution over time and troublesome contexts and cues around which counseling will be focused. These will be handed to participants after sessions or emailed or mailed to participants (based on the participant’s preference) after some calls. While the emphasis will clearly be on skill acquisition and execution, the targeting of skills for individual participants will be done in a collaborative manner. There will be praise for any progress and a collaborative determination of barriers to skill execution. Thus, coping and avoidance plans will be: 1) collaboratively developed, 2) given/ sent to patients immediately after any contact where plans are developed, and 3) reviewed carefully at future contacts to refine coping plans. The key elements of this counseling will be specific, individualized coping plans, monitoring of plan execution and effects, and on-going modification of plans.

*Supportive Therapy.* This intervention will comprise elements and content consistent with the characterization of intra-treatment support as contained in the PHS Clinical Practice Guideline (Fiore et al., 2008). Thus, it will involve encouragement (e.g., information that previous failure to quit is often positively related to subsequent success), a focus on short-term goals (e.g., go without smoking for 2 hours, communication of belief in the participant’s ability to quit), discussion of participant values (what the participant feels would be good and healthy for them in the long run) and how these values are congruent with cessation, emphasis on the patient and the counselor being a team, encouragement for the participant to generate a quitting strategy with the message that smokers often have a good sense of what will work for them (a client centered approach), and prompts for the participant to explore his/her feelings about quitting and feelings of optimism and concern; i.e., to use the counselor as a sounding board. Therefore, the Skill Training approach emphasizes explicit training while the Supportive intervention does not. Because these two forms of therapy may co-occur, counseling manuals will be carefully prepared so as to permit their effective integration. For instance, while the Skill Training intervention will recommend coping skills for the participant, when the participant also receives Supportive counseling s/he will be encouraged to discuss his/her feelings about the quit plan and reflect on its “fit” for his/her life.

*Medication.* All participants will receive 8-weeks of combination NRT (nicotine patch + nicotine mini-lozenge). Nicotine patch dosing will be based on current cigarettes smoked per day, per package insert: for those who currently smoke >10 cigs/day=4 weeks of 21 mg, 2 weeks of 14 mg, and 2 weeks of 7 mg nicotine patches, along with nicotine mini-lozenges; for those who currently smoke <=10 cigs/day=6 weeks of 14 mg and 2 weeks of 7 mg nicotine patches along with mini-lozenges. Mini-lozenge dosing will be based on how soon participants currently smoke after waking before their initial quit attempt and will be consistent with the package insert (4 mg for participants who smoke within 30 minutes of waking and 2 mg for participants smoke more than 30 minutes after waking).

“Breaking Addiction to Tobacco for Health (BREATHE) Study”

PI: [name], MPH, MBA; UW-CTRI Center Grant: 1P01CA180945-01.

**Clinic Randomized Control Trial**

**Implementation.** The clinics assigned to the experimental condition will have the EHR enhancements introduced by methods we have used previously to introduce healthcare upgrades into clinics (including EHR enhancements). These procedures include staff training visits, follow-up calls, and feedback on EHR use and treatment referral. Importantly, clinic training will be standardized across clinics. The great majority of the clinics assigned to the control condition will already be participating in the Fax-to-Quit (F2Q) program. However, all clinics (including those already using the F2Q program) will be given implementation training to ensure that all clinics start with similar implementation support. The minimum implementation training will be one initial staff meeting and a second meeting at six months to provide feedback, encouragement, and promote problem solving). Also, as per good clinical practice, if notable problems are observed in smoker identification and referral data coming from a clinic, ad hoc problem solving via phone calls or meetings will be undertaken with the clinic to resolve obstacles. Such ad hoc problem solving will occur with clinics in both conditions and will be recorded so as to permit comparison of needed implementation support.

Certain additional procedures will be used in the active (non-control) clinics. Prior to the EHR modifications and initiation of participant recruitment in a given clinic, an in-service training will take place, attended by UW-CTRI research staff, clinic physicians, and other clinical and support staff. These trainings will be scheduled during one of the clinic's existing staff meetings. Trainings will include a description of the study protocol relevant to clinic staff and an overview of the goals of the project and the role of the clinic personnel in achieving these goals. Past experience has demonstrated the importance of both [name] (as study PI) and the clinic Medical Director attending these launch training meetings for each clinic (i.e., 18 meetings in the proposed Program Project). Their joint attendance at the meetings increases staff attendance and highlights how important the project is to the clinic and healthcare system. These launch meetings will include a walk-through of the new EHR functions (including EHR screen-shots), emphasizing their ease of execution and how they will enhance patient care. The training will also clearly describe the roles of clinic personnel in the research/treatment project and explain how their activities benefit the patient and the project. We will then answer any questions and address concerns. Because the roomers will play a pivotal role in using the enhanced EHR functions (e.g., smoking documentation, referral), we will arrange additional meetings with these key clinic staff members to continue training, answer questions and enhance their commitment. These additional trainings with roomers often involve a lunchtime meeting where the UW-CTRI research staff brings lunch. UW-CTRI staff will conduct the research interventions for the clinical projects at the clinic sites and therefore will be available throughout the study, providing refresher training once every other month and regular quality/progress reports to the clinic.

About a week after this introduction and launch of the EHR enhancements in each clinic, UW-CTRI research staff assigned to the clinic will follow-up with the clinic manager to address questions, problem solve, provide early performance feedback on smoker identification and recruitment, and reinforce proper EHR use. Over the next 3 weeks, UW-CTRI research staff will work with each clinic manager, as well as healthcare system database personnel, to examine de-identified data to ensure that clinic staff are using the new EHR resources properly. We will record all instances where we intervene and train with clinics in order to identify and document best practices training recommendations. When problems come to light, we will work

“Breaking Addiction to Tobacco for Health (BREATHE) Study”

PI: [name], MPH, MBA; UW-CTRI Center Grant: 1P01CA180945-01.

collaboratively with the clinic manager and roomers (and occasionally the Medical Director and other medical staff) to support proper EHR use and smoker referral. These training and feedback systems have been used successfully by UW-CTRI research staff in more than a dozen prior NIH studies and by UW-CTRI staff who have trained over 10,000 clinicians across Wisconsin in tobacco intervention as part of the Center’s statewide outreach mission.

***Smoker identification and referral in clinics.*** Therefore, in control clinics, clinic personnel will use methods consistent with good clinical practice, and that very similar to those currently in use in such clinics, to identify smokers, document their smoking status, and refer them to the WTQL (and possibly to other resources such as the patient’s primary care physician). These methods include using existing EHR resources to identify smokers (e.g., the expanded vital signs) and to document their smoking status, and then use the standard paper fax-to-quit methods to refer patients to the WTQL. As is typical of current practice (and distinct from a chronic care approach) *only those patients who are interested in cessation will be referred to the WTQL* (not those interested in reducing their smoking). These methods will be compared with the EHR methods that will be used in the experimental clinics and that are described above, with both the F2Q and EHR methods having comparable levels of implementation support.

**Data Collection: Questionnaire, Interview, and Behavioral Assessments for the Clinical Studies and Data Collection for the Clinic Randomized Control Trial**

Part of the synergy of this research arises from the use of consistent assessments across all three research studies. This consistency will allow us to compare participants and events across all three samples – including allowing us to compare smokers who are and are not motivated to quit and smokers who do and do not relapse. Assessments, which have good to excellent psychometric characteristics, will include: 1) individual difference variables related to outcome; 2) potential mediators of intervention component effects; and 3) proximal and distal outcomes. At Visit 1 participants in all 3 studies will complete a standard baseline assessment that includes: tobacco use history, demographic assessments, exhaled carbon monoxide assessment, height and weight assessment, tobacco dependence assessed via the Brief Wisconsin Inventory of Smoking Dependence Motives (WISDM-34) and the Fagerström Test of Nicotine Dependence (FTND), affect assessed using the well-validated Positive and Negative Affect Scale (PANAS), withdrawal assessed using the Wisconsin Smoking Withdrawal Scale (WSWS), and motivation and self-efficacy assessed using Likert scale items used in previous research. Participants will also evaluate the treatment provided in terms of burden and acceptability as well as their perceptions of the healthcare system for providing such treatment, using measures developed for this study based on previous research on patient satisfaction assessments. Specifically, we will assess constructs such as satisfaction with study staff, clinic staff for referring the smoker to the study, and the healthcare system for providing the treatment. Consistent mediators assessed across the 3 projects include motivation, self-efficacy, and withdrawal. There will also be study-specific baseline and follow-up assessments, as described below.

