**Clinic Randomized Control Trial**

**Primary Aim:** Using a multiple baseline design, determine the effects of a healthcare intervention package comprising a comprehensive set of EHR-based enhancements and a chronic care treatment for smoking, on rates of documentation of smoking status, referral to smoking treatment, and engagement in smoking treatment as compared to a usual care fax-to-quit referral to the Wisconsin Tobacco Quit Line.

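### Clinic trial: implementation support is called comparable, but the protocol schedules much more of it for experimental clinics, so a difference cannot be credited to the EHR enhancements and chronic care treatment under matched support

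*Combined protocol and SAP*

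**What the plan says.** All places are in the combined protocol and SAP.

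- **The Intervention Components, Clinic Randomized Control Trial, Implementation (all clinics).** All clinics "will be given implementation training to ensure that all clinics start with similar implementation support". The guaranteed amount is a floor: "The minimum implementation training will be one initial staff meeting and a second meeting at six months". Help with observed problems is open to both arms: "Such ad hoc problem solving will occur with clinics in both conditions and will be recorded so as to permit comparison of needed implementation support".
- **Same section, next paragraph.** "Certain additional procedures will be used in the active (non-control) clinics". These are a launch in-service, further meetings with roomers, and research staff present through the study and "providing refresher training once every other month and regular quality/progress reports to the clinic". The text describes the principal investigator and the clinic Medical Director both "attending these launch training meetings for each clinic (i.e., 18 meetings in the proposed Program Project". Eighteen is the upper limit for experimental clinics, not the total of up to 28 clinics. The paragraph after that adds a follow-up with the clinic manager about a week after launch, with early performance feedback, and then three weeks of reviewing de-identified data.
- **Smoker identification and referral in clinics.** After these paragraphs, the two methods are described "with both the F2Q and EHR methods having comparable levels of implementation support".
- **Analytic Plans, Clinic Randomized Control Trial, Primary Aim.** The tested package is described as "comprising a comprehensive set of EHR-based enhancements and a chronic care treatment for smoking". Under Data Collection for the Clinic Randomized Control Trial, Post-intervention data, the design is said to reflect increases due to those same two elements. Neither place names training or feedback.

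**The concern.** The comparability clause is a statement about the design. A reader who relies on it will take a difference in treatment engagement, the primary outcome, as the effect of EHR enhancements plus chronic care treatment over fax referral, with support held equal.

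The extra support is aimed at the steps that produce the outcomes. The protocol describes roomers as central to documentation and referral, and the early feedback concerns smoker identification and recruitment. Referral leads to engagement. The documents give no estimate of how much training and feedback alone would move these rates, but they give no ground for treating the contribution as zero.

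At stake is what the trial may conclude and what a health system should expect. A system that installed the EHR build and offered the treatment, but not the repeated training and reports, would not be reproducing the tested condition.

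**Working it through.** **1. The plan's own figure.** The power section for the clinic trial uses the clinic as unit, SD 4 and alpha .05. It gives power above .998 for a difference of 8 points (10% vs 2%; 18 vs 10 clinics) and .887 for 6 points (8% vs 2%; 10 vs 10 clinics). A two-sided two-sample t-test with noncentrality d / (SD × √(1/n1 + 1/n2)) gives:

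- 18 vs 10: 8 / (4 × √(1/18 + 1/10)) = 5.07 on 26 df, power 0.9982.
- 10 vs 10: 6 / (4 × √(1/10 + 1/10)) = 3.35 on 18 df, power 0.8870.

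Both reproduce. For a pre-post change score the same values hold if the pre-post correlation is 0.5, since the change SD is then 4 × √(2 × (1 − 0.5)) = 4. This is power for the total difference between arms, whatever its source. It neither depends on the support question nor answers it.

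**2. Scheduled contacts per clinic.** Experimental clinics take part for at least 16 months, with control duration yoked (Study Design, Clinic Randomized Control Trial). Refreshers every two months give 16 / 2 = 8, or 7 if none is held at the close. The number of roomer meetings (1 to 2) and of data-review contacts (0 to 3) is not stated and is assumed.

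| Item | Control, guaranteed | Experimental, low | Experimental, high |
|---|---|---|---|
| Initial staff meeting | 1 | 0 (counted as the launch) | 1 |
| Month-six meeting | 1 | 0 (counted as a refresher) | 1 |
| Launch in-service | 0 | 1 | 1 |
| Roomer meetings | 0 | 1 | 2 |
| One-week follow-up | 0 | 1 | 1 |
| Data-review contacts | 0 | 0 | 3 |
| Refreshers | 0 | 7 | 8 |
| **Total** | **2** | **10** | **17** |

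The ratio to the control floor runs from 10 / 2 = 5 to 17 / 2 = 8.5. If the launch is the initial meeting and the month-six meeting is separate, the range is 11 to 16, or 5.5 to 8 times. Progress reports, on-site presence and ad hoc contacts are left out.

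**3. Without the assumed items.** The refreshers alone (7 to 8) exceed the 2 guaranteed control contacts. A clinic that left early would have had 6 / 2 = 3 refreshers by month six.

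**4. Can the analysis separate support from the package?** The ANCOVA covariates are location, size, SES and baseline documentation and referral rates. Support received is not among them. Adding it would help little, because scheduled support is almost fixed by arm. The share of the expected 8-point difference that is due to support therefore cannot be identified from this design.

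**The case against.** The best defence is that training is openly part of how the intervention is delivered. The Study Overview speaks of EHR enhancements together with related healthcare practices. The Implementation paragraph says the enhancements are introduced through training visits, follow-up calls and feedback. The post-intervention period starts only after training and implementation. The EHR and chronic care elements are already bundled, so no single-component effect was on offer. All of this stands, and it defeats two inferences a reader might draw: that the extra support is hidden, and that the trial is invalid. The extra procedures are disclosed, and the randomized contrast of the whole package with fax-to-quit is sound.

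Second, not all of the extra contact is separable support. The launch includes a walk-through of new EHR functions and staff roles in the study, and most control clinics already use fax-to-quit. Research staff are on site because they deliver the chronic care treatment. This also stands. It does not cover refreshers and progress reports continued through participation.

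Third, two control meetings are a minimum, ad hoc help can add to them, clinics may leave before 16 months, and the count gives a brief follow-up and a full staff meeting equal weight. The ratio is therefore one of scheduled contacts against a floor. It should not be read as a five- to eight-fold difference in intensity, or as the source of a given part of the effect.

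Fourth, a reader might infer that only ad hoc contacts are logged. That is not so: the protocol also records every instance of intervening and training with clinics. However, that sentence sits in the text on active clinics and its stated purpose is best-practice recommendations. Comparison between arms is mentioned only for ad hoc help.

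None of this rescues the comparability clause. A promise that clinics start with similar support is narrower than an unqualified statement that the methods have comparable support, and even at the start only experimental clinics get the launch, roomer meetings and one-week feedback.

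**Conclusion.** The concern holds in a limited form. The comparability clause is wrong on the protocol's own schedule: roughly 10 to 17 scheduled contacts in experimental clinics against a guaranteed 2 in control clinics over 16 months. The range rests on the assumed numbers of roomer and data-review contacts and on how overlapping meetings are counted. That the refreshers alone exceed the control guarantee rests on neither.

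The consequence is for interpretation. A difference in engagement can be credited to the package as delivered, training and feedback included. It cannot be credited to EHR enhancements and chronic care treatment under matched support, as the clause, the Primary Aim and the Post-intervention data text together imply. No power or sample-size figure changes. The documents do not show how much of the expected difference comes from support.

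**What to change.** 1. In Smoker identification and referral in clinics, replace the comparability clause with a statement that scheduled support differs by arm as the preceding implementation paragraphs describe.
2. In Post-intervention data and in the Primary Aim, define the experimental package as EHR enhancements, chronic care treatment, and its implementation training and feedback. Define the comparator as fax-to-quit with the minimum implementation training and ad hoc support given to all clinics. It should not be called fax-to-quit with two meetings, because two is a floor. Limit the conclusion to that package against that comparator.
3. Make one contact log cover scheduled and ad hoc contacts in both arms, and report it by arm beside the primary result. Ad hoc contacts in both arms and training contacts in active clinics are already recorded, so the addition is mainly the control clinics' scheduled meetings and the report by arm.

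The cost is a slightly narrower claim and minor logging work. No clinics, patients or staff are added.
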